9.3.2 Outcomes

9.3.2.1 Primary outcome

The main outcome measure of our study is the incidence of dose reduction/interruption, calculated separately for each drug. For calculating the primary outcome, we will first need to calculate the average daily dose of pirfenidone and nintedanib after drug initiation (post-index period). Specific details of calculations are —

Average daily dose

Average daily dose for each patient will be calculated by taking the average of total drug intake (tablet strength * number of doses) during the time between index date to the date of drug discontinuation

```
Average \ Daily \ Dose \\ = \frac{\sum_{0}^{n}(Tablet \ Strength*number \ of \ tablets \ in \ a \ Rx \ fill)}{Time \ of \ follow - up \{(Date \ of \ discontinuation) - Index \ Date\}} Where n = number of fills a patient has received for pirfenidone/nintedanib
```

- We will calculate average daily dose of pirfenidone and nintedanib separately for each month in post-index period (month 1 to 12) and will also calculate for cumulative periods of 6 months and 12 months. For all calculations, censoring events will be taken into account, with patient censored at the date of drug discontinuation, or end of 12 months.
- Six and twelve months average daily dose categories For the average daily dose calculations in cumulative periods, we will be dividing the patients in following 4 categories
 - 1) Dose strength less than 50%
 - 2) Dose strength between 51% to 66%
 - 3) Dose strength between 67% to 90%
 - 4) Dose strength above 90%

Incidence of Dose Reduction and/or temporary dose interruption

Once average daily dose is calculated for each month post-index (month 1 to 12), incidence of dose reduction/interruption will be calculated as presence of average daily dose $\leq 90\%$ dose strength (for pirfenidone) or $\leq 66.67\%$ dose strength (for nintedanib), as per the PI [12 – 14]. Patients will be required to have the dose reduction for at least for 60 days, to make sure that the dose reduction is not temporary.

In a sensitivity analysis, we will also evaluate temporary dose reductions, i.e., dose reduced to below the above defined dose strength only for 1 month.

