9.3.2.2 Secondary outcomes

We will assess drug discontinuation as a secondary outcome. Pirfenidone or nintedanib discontinuation will be defined as presence of sixty or more days gap in refilling a prescription of the drug (sixty days gap counted from the date of last fill plus the days of supply for the fill). The date of last fill plus the days of supply for the fill (typically 30 days) will be designated as date of discontinuation, and time to discontinuation will be calculated as time between date of discontinuation and index date (only for patients who discontinue the drug). We will calculate the percentage of patients who discontinue each drug in first 6- and 12-months post-index period. As a sensitivity analysis, we will calculate drug discontinuation using 30 days and 90 days as allowed gap between the scripts (vs. 60 days)

We will also assess how many patients initiate either of the antifibrotic drugs (including the same drug the patient has discontinued) during the follow-up time post discontinuation of their index drug. We will separately assess initiation of the index drug vs. initiation of the other antifibrotic agent.

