9.7 DATA ANALYSIS

9.7.1 Main analysis

Baseline characteristics for the pirfenidone and nintedanib cohorts will be reported as frequencies with percentages for categorical data, and means with standard deviations (SD), and median with interquartile range will be reported for continuous variables. We will compare the baseline characteristics using Student's T-test or Wilcoxon rank-sum test for continuous variable, and chi-square test for categorical variable

Average daily dose during first 6 months and 12 months after drug initiation will be reported as means with standard deviations (SD), and median with interquartile range. Six months and 12-months daily dose categories will be presented as frequencies with percentages. Incidence of dose reduction will be reported by month of occurrence (using month 2 and onwards) and reported as frequencies with percentages. Time to drug dose reduction will be reported in months (mean (SD)). Drug discontinuation will be reported as frequencies with percentages, and time to drug discontinuation will be reported in months (mean (SD)). As this is a descriptive study, there will be no multivariable adjustment and/or direct comparison of outcomes between the pirfenidone and nintedanib cohort.

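### The 6- and 12-month average daily dose is a dose while on treatment, but it is labelled as dose over the period and pools patients regardless of time on drug

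*Combined protocol and SAP*

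**What the plan says.** Section 9.3.2.1 defines each patient's average daily dose as milligrams dispensed divided by the time from index to discontinuation; the average is taken "during the time between index date to the date of drug discontinuation". Besides the monthly values, the study "will also calculate for cumulative periods of 6 months and 12 months". All these calculations are censored, "with patient censored at the date of drug discontinuation, or end of 12 months".

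Section 9.3.2.2 defines discontinuation as "presence of sixty or more days gap in refilling a prescription of the drug". It dates the event back to the end of supply: "The date of last fill plus the days of supply for the fill (typically 30 days) will be designated as date of discontinuation".

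For the cumulative averages, 9.3.2.1 states: "For the average daily dose calculations in cumulative periods, we will be dividing the patients in following 4 categories". The highest is "Dose strength above 90" percent. Section 9.7.1 adds: "Six months and 12-months daily dose categories will be presented as frequencies with percentages". The Abstract and 9.7.1 describe the mean and median as the dose over the first 6 and 12 months after initiation, and neither says that it is a dose while on drug. Section 9.3.2.1 plans an analysis of patients who never discontinue, but only for the incidence of dose reduction and not for the average dose or its categories.

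**The concern.** The days without drug that define stopping never enter the denominator. For anyone who discontinues, the 6-month or 12-month figure describes only the time on drug, which may be 30 days. A reader of 9.7.1 would take it as dose over the whole period.

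The four categories count each patient once, have no level for discontinued patients and are not split by discontinuation status. A patient with one month of drug and a patient with twelve can sit in the same cell. Discontinuation is reported elsewhere, but the two results are not linked, so nobody can tell how much of the top category is short exposure. Section 7 says that the study may reveal sub-optimal dosing among patients who have not stopped. The pooled table cannot isolate those patients.

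**Working it through.** **Inputs.** The formula and censoring come from 9.3.2.1; the discontinuation date, the 60-day gap and the typical 30-day supply come from 9.3.2.2. Full doses of 2403 mg (pirfenidone) and 300 mg (nintedanib) come from section 7. Its thresholds reproduce: 2165/2403 = 90.1% and 200/300 = 66.67%. The percentages below are relative to full dose, so they apply to both drugs. Assumptions: 6 months = 180 days and 12 months = 360 days unless 365 is shown, and fills after discontinuation are not counted.

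**Step 1: patients who stop.** The plan's value is (supply days × fraction of full dose) / (end of last supply − index date). The last two columns divide the same milligrams by the fixed period.

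| Fill history, then stop | Plan's formula | Over 180 days | Over 360 days |
|---|---|---|---|
| 1 full-dose fill | 30/30 = 100% | 30/180 = 16.7% | 30/360 = 8.3% |
| 2 full, on time | 60/60 = 100% | 33.3% | 16.7% |
| 5 full, on time | 150/150 = 100% | 83.3% | 41.7% |
| 3 full, each refill 10 days late | 90/110 = 81.8% | 50.0% | 25.0% |
| 2 full, 1 at two-thirds | 80/90 = 88.9% | 44.4% | 22.2% |
| 3 at two-thirds | 60/90 = 66.7% | 33.3% | 16.7% |

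The plan's value is the same at 6 and 12 months for each of these patients. The first three rows fall in the top category; the last three do not.

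**Step 2: comparison with patients who stay on drug.** Take full-dose 30-day fills, each refilled *d* days late. A patient who stops after *k* fills scores 30*k* / (30*k* + (*k* − 1)*d*).

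- *d* = 5, stoppers: *k* = 1, 100%; *k* = 2, 60/65 = 92.3%; *k* = 3, 90/100 = 90.0%; *k* = 6, 180/205 = 87.8%; *k* = 10, 300/345 = 87.0%.
- *d* = 5, continuers, last fill cut at the period end: 155/180 = 86.1% and 315/365 = 86.3%.
- *d* = 5, continuers, last fill counted whole: 180/180 = 100% and 330/365 = 90.4%.
- *d* = 3, continuers, last fill cut: 165/180 = 91.7% and 332/365 = 91.0%. Stoppers are also above 90%, since the formula stays above 30/33 = 90.9%.
- *d* = 7: a two-fill stopper scores 60/67 = 89.6%, below the top category.

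Section 9.3.2.1 does not say which way the last fill is counted. At *d* = 5, cutting it puts one- and two-fill stoppers above continuers. Counting it whole puts continuers in the top category and stoppers after three or more fills below it.

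**Step 3: what the label could hide.** Suppose 10% to 50% of patients stop, with stop times even over months 1 to 11 and everyone at full dose without gaps. The plan's 12-month mean is 100%, with every patient in the top category, whatever the share who stop. Over the fixed period, stoppers average (1 + … + 11)/(11 × 12) = 50% of full dose, and 10 of the 11 stop times give 90% or less. The mean is then 95% down to 75%, and the top category holds 1 − 0.1 × 10/11 = 90.9% down to 1 − 0.5 × 10/11 = 54.5%. The shares are assumed; the documents give no discontinuation rate.

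**The case against.** Dose while on treatment is a legitimate descriptive quantity. The censoring is stated openly, and discontinuation is a secondary outcome with its own percentages and time to event. The main outcome is the incidence of dose reduction from monthly doses, which 9.3.2.1 also evaluates in never-discontinuers. All of this stands, and it makes the defect one of labelling and tabulation. It does not remove the mismatch in 9.7.1 or the pooling of unequal exposure.

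A reader might also infer stronger conclusions that the documents do not support:

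- *Early stoppers are placed in the top category.* This is true only for full-dose fills refilled nearly on time, as Step 1 shows.
- *Poorer persistence makes the dose result look better.* Step 2 shows that this depends on the refill delay and on an unstated rule for the last fill, and that it can reverse.
- *A known share of the top category is one-month patients.* The plan gives no such rate.
- *The pooling biases a comparison of the two drugs.* Sections 9.1 and 9.7.1 plan separate reporting without direct comparison of outcomes; the matched reanalysis in 9.7.2 is contingent.

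That dispensed drug may not have been taken is already listed in 9.9 and is inherent to claims data.

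Missing follow-up does not justify the label: 9.2.2 requires 12 months of post-index enrollment for the 12-month analysis, so fills can be observed throughout.

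**Conclusion.** The point holds as a mismatch between label and measure, together with a pooling of unequal exposure. For one patient with a single full-dose 30-day fill, the reported value is 100% at both time points, against 16.7% and 8.3% over the fixed periods. This follows from the definitions in 9.3.2.1 and 9.3.2.2 and needs no assumption about refill delay or the last fill, only 180 and 360 days for the fixed periods.

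The effect on the whole distribution cannot be sized from the documents. For a stopper, the on-treatment value exceeds the fixed-period value. Whether stoppers sit above or below continuers in the plan's table is undetermined. The measure itself need not be replaced.

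**What to change.** In 9.3.2.1 and 9.7.1, and in the matching Abstract text, name the measure average daily dose while on treatment. Report the mean, median and four categories in two columns:

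- patients still on the index drug at 6 or 12 months;
- patients who discontinued before then, with their median time on drug.

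Keeping the stoppers' dose distribution in its own column preserves the dose they received before stopping. State in 9.3.2.1 how a fill that runs past the period end is counted.

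The cost is one cross-tabulation by discontinuation status, which is already derived, and smaller cells. The column of patients still on drug is selected on a post-index event and should be described as such.

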8. RESEARCH QUESTION AND OBJECTIVES

The overarching aim of our study is to assess the incidence of dose reduction and discontinuations separately for pirfenidone and nintedanib. Specific objectives are:

Primary aim - To assess average daily dose, and corresponding dose reduction/interruption patterns in pirfenidone initiators and nintedanib initiators separately at 6- and 12- months post-initiation.

Secondary aim - To assess drug discontinuation patterns in pirfenidone initiators and nintedanib initiators separately at 6- and 12-months post-initiation.

001-MCS-90-118_RD-23 (1.0) / Saved on: 25 Nov 2019

NIS Protocol Page 15 of 36

Study number: 1199-0526 Document number: c41847952-01

Proprietary confidential information © 2023 Boehringer Ingelheim International GmbH or one or more of its affiliated companies

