In the primary analysis, patients who reduce their dose in the prior months will be allowed to discontinue the drug in future months (For example, in primary analysis, a patient can reduce their index drug dose in month 2 (i.e. dose below label recommendation for the whole month 2 and 3), and then can discontinue the drug in month 4 (or beyond). We will also evaluate the incidence of dose reduction in patients who never discontinue the index drug.

NIS Protocol Page 19 of 36

Study number: 1199-0526 Document number: c41847952-01

Proprietary confidential information © 2023 Boehringer Ingelheim International GmbH or one or more of its affiliated companies

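### The average daily dose formula in 9.3.2.1 has no rule for cutting supply at the end of the 6- or 12-month period, so cumulative dose in patients still on drug is unchanged or too high, never too low

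*Combined protocol and SAP*

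**What the plan says.** Section 8 puts the measure in the primary aim: "Primary aim - To assess average daily dose, and corresponding dose reduction/interruption patterns in pirfenidone initiators and nintedanib initiators separately".

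Section 9.3.2.1 describes it in prose as the average of "total drug intake (tablet strength * number of doses) during the time between index date to the date of drug discontinuation". The formula beneath sums strength times number of tablets over the fills and divides by the time from index date to discontinuation. Its index is defined by "Where n = number of fills a patient has received for pirfenidone/nintedanib".

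The same section applies the measure to each month and says that the study "will also calculate for cumulative periods of 6 months and 12 months". It adds: "For all calculations, censoring events will be taken into account, with patient censored at the date of drug discontinuation, or end of 12 months". The cumulative doses are sorted into four categories, with one boundary at 90%. Section 9.7.1 reports them as mean, median and category frequencies.

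Section 9.3.2.2 fixes the end of treatment: "The date of last fill plus the days of supply for the fill (typically 30 days) will be designated as date of discontinuation".

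**The concern.** The numerator counts tablets dispensed and the denominator counts days followed. The ratio is a daily dose only if both cover the same days. Nothing in the formula or in the definition of n ensures this for a patient whose follow-up ends at a calendar cut and not when the supply runs out.

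Three things are at stake:

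- The error goes one way only.
- It falls on patients still on drug and not on those who discontinued before the cut.
- For the same number of overhanging days, it is about twice as large relative to a 6-month period as to a 12-month one. The reported dose could therefore appear to fall between 6 and 12 months with no change in use.

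**Working it through.** The documents give no average-daily-dose result, so there is no figure to reproduce. The check applies the formula and compares it with supply falling inside the period.

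**Inputs from the protocol.** A fill typically covers 30 days (9.3.2.2). The cumulative periods are 6 and 12 months (9.3.2.1). One dose category ends at 90% and the next lies above it (9.3.2.1).

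**Assumptions.** Fills are full-strength and refill intervals are regular. The documents give no refill data. Period length is not stated in days, so two conventions are used. One is 180 and 360 days, in line with 9.3.2.1, where a reduction must last 60 days ("Patients will be required to have the dose reduction for at least for 60 days") and the example is "dose below label recommendation for the whole month 2 and 3". The other is the calendar convention of 183 and 365 days. Only fills dated before the cut are counted.

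**Formulas**, for a patient still on drug at cut W, with k fills dated before W:

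- Formula as written: 30k / W.
- Supply inside the period: (sum over fills of the supply days before W) / W.

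**Patient who discontinues before the cut.** With fills on days 0, 30 and 60, the discontinuation date is day 90 and the formula gives 90/90 = 100%. No part of the last fill lies beyond follow-up.

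**Limit for one overhanging fill.** A fill collected on the last day before the cut leaves 29 days outside: 29/180 = 16.1% and 29/360 = 8.1% (29/183 = 15.8% and 29/365 = 7.9%).

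**Patients still on drug:**

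| Refill every | W (days) | Fills | As written | Inside the period |
|---|---|---|---|---|
| 30 days | 180 | 6 | 180/180 = 100.0% | 180/180 = 100.0% |
| 30 days | 183 | 7 | 210/183 = 114.8% | 183/183 = 100.0% |
| 30 days | 360 | 12 | 360/360 = 100.0% | 360/360 = 100.0% |
| 30 days | 365 | 13 | 390/365 = 106.8% | 365/365 = 100.0% |
| 34 days | 180 | 6 | 180/180 = 100.0% | (5×30+10)/180 = 88.9% |
| 34 days | 360 | 11 | 330/360 = 91.7% | (10×30+20)/360 = 88.9% |
| 35 days | 180 | 6 | 180/180 = 100.0% | (5×30+5)/180 = 86.1% |
| 35 days | 360 | 11 | 330/360 = 91.7% | (10×30+10)/360 = 86.1% |
| 36 days | 180 | 5 | 150/180 = 83.3% | 150/180 = 83.3% |
| 36 days | 360 | 10 | 300/360 = 83.3% | 300/360 = 83.3% |

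The 34- and 35-day patterns move from the 67–90% category to the one above 90%, in both periods. Among regular whole-day intervals from 28 to 60 days, they are the only ones that do so at 180 and 360 days. At 183 and 365 days, 34, 35 and 36 days do.

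**Irregular refills.** Simulated whole-day intervals with mean 30 and SD 3 days (assumed), all patients still on drug, gave these mean doses:

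| W (days) | As written | Cut at W, no overlap rule | Cut at W, early-refill stock carried forward |
|---|---|---|---|
| 180 | 107.9% | 100.1% | 97.9% |
| 360 | 104.0% | 100.0% | 98.2% |

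The smallest individual excess was 0 and none was negative. When refills are early, more than one fill can overhang the cut. The excess over a simple cut at 180 days reached 38 days in one run, so 29 days limits one fill and not the total.

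**The case against.** The strongest reply is that this is a gap in specification and not a wrong sum. The prose speaks of intake during a stated interval, and censoring is to be taken into account in all calculations. The formula is also used for single months, where summing every fill would be meaningless, so some restriction to the period must be intended. A sensible programmer might trim the tablets too.

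Part of this stands. The prose can be read as a limit, and the check above already relies on a mild reading by dropping fills dated after the cut. The 6-month end point is itself inferred, since the censoring sentence names only 12 months. But that sentence says when follow-up ends and not which tablets count, and neither the formula nor the definition of n trims the last fill. Two programmers could each claim to follow the text and report 100.0% and 86.1% for the same patient.

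The limitation in 9.9, that fill-derived dose may differ from actual intake, does not disclose an error in one known direction. That the study is descriptive does not remove the point either, because these summaries are among its results.

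The category shifts do come from a narrow set of assumed intervals. They show that a shift is possible, not that it is common.

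**Conclusion.** The point holds for the cumulative 6- and 12-month average daily dose. Applied as written, the formula gives patients still on drug a value that is correct or too high and never too low, relative to supply inside the period. The excess is zero for some patterns. With 30-day fills it is at most 16.1% of 180 days or 8.1% of 360 for one overhanging fill, and more where early refills accumulate.

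These sizes rest on the typical 30-day fill and on assumed refill intervals and period lengths. The cohort-wide size is unknown, because the documents give neither refill data nor the share of patients still on drug at each cut.

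A reader might infer that the main outcome, incidence of dose reduction or interruption, is biased as well. The documents do not support that: the outcome is built from monthly averages, no rule for allocating fills to months is given, and no effect on it is shown here. A reader might also infer that many patients change dose category. That cannot be concluded from a few chosen intervals.

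The correction should be made before analysis, because the measure is in the primary aim and the change is cheap.

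**What to change.** In 9.3.2.1:

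1. Spread each fill's tablets over its days of supply.
2. Count only supply days that fall inside the period.
3. Set the denominator to the earlier of the discontinuation date (as defined in 9.3.2.2) and the end of the 6- or 12-month period, minus the index date.
4. State the periods in days, consistently with the protocol's equation of 60 days with months 2 and 3.

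Handling of overlapping supply from early refills is a separate choice, which the sponsor should state. Carrying stock forward keeps a patient from exceeding the dispensed daily dose. It would understate dose where an early refill reflects a real increase, so the rule should also cover changes in strength or tablets per day.

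The cost is a few lines of text and code, with no new data. Reported cumulative doses for patients still on drug will be lower wherever supply overhangs the cut.

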7. RATIONALE AND BACKGROUND

Idiopathic pulmonary fibrosis (IPF) is a life-threatening rare disease characterized by decline in lung function due to progression of fibrosis in the interstitium of the lung [1]. In patients with IPF, a decline in forced vital capacity (FVC) is an important indicator of mortality [6]. The median survival of non-treated IPF patients is approximately 3 years from diagnosis [2].

[figure not shown]
Before anti-fibrotic medications became available in the US, IPF treatment mainly consisted of therapeutics that were found not to be of benefit (or even harmful), and a mainstay of care focused on symptom relief and included palliative care [3]. In October 2014, two anti-fibrotic medications, nintedanib and pirfenidone, were approved by the U.S. Food and Drug Administration (FDA) for the treatment of IPF [4, 5], which transformed the treatment of this disease. Both medications were found to reduce the rate of decline in FVC compared to placebo in phase III clinical trials [7, 8].

From the perspective of treatment, the approvals of antifibrotics for IPF were significant breakthroughs. Antifibrotics have demonstrated an ability to slow IPF progression, if taken according to the recommended dosing in the prescriber information and taken continuously, in both clinical trials [7, 8] and real-world evidence [9]. Previous real-world studies have compared persistence/ discontinuation patterns for pirfenidone and nintedanib and found similar persistence patterns for both drugs [10, 11]. However, these studies have failed to consider the differential dosing regimens between these two drugs and corresponding incidence of dose reduction and/or temporary dose interruption. Hence, this study will assess both dose reduction and/or temporary dose interruption and discontinuation patterns for pirfenidone and nintedanib among patients with IPF.

In this study, we will investigate the incidence of dose reduction/interruption beyond the label recommendations (defined as a dose not following the prescriber information (PI), which corresponds to a daily dose of 2165 mg (90% of full dose, which is 2403 mg) for pirfenidone [12, 13] or less than a daily dose of 200 mg for nintedanib (66.67% of full dose, which is 300 mg) [14]) from 10/01/2014 to 09/30/2022 using real-world data. The definition of incidence of dose reduction, which is differential for nintedanib and pirfenidone is because of –

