- 1) In the US, the prescriber information (PI) and/or label for pirfenidone does not indicate any particular dose reduction recommended as per Food & Drug Administration (FDA). For nintedanib, reducing dose from 150 mg to 100 mg BID is part of the PI.
- 2) The post-hoc analysis of clinical trials showed similar slope of FVC decline for patients who reduced the dose to 100 mg BID for nintedanib, but for pirfenidone, the slope of FVC decline was steeper for patients who reduced the dose, potentially indicating that reduced dose might lead to lower benefit on FVC decline (see figures below) [12, 15]

Proprietary confidential information © 2023 Boehringer Ingelheim International GmbH or one or more of its affiliated companies

The current study may be able to demonstrate to decision makers the differential complexities in dosing regimen for pirfenidone vs. nintedanib and may reveal that IPF patients may not be receiving the full benefit of pirfenidone due to possible sub-optimal dosing, even when the patient has not discontinued the drug.

NIS Protocol Page 14 of 36

Study number: 1199-0526 Document number: c41847952-01

Proprietary confidential information © 2023 Boehringer Ingelheim International GmbH or one or more of its affiliated companies

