The main outcome of our study will be incidence of dose reduction/interruption, calculated separately for pirfenidone and nintedanib. For each patient, average daily dose will be calculated in pre-specified time-periods (for example – the first 6 months, the first 12 months, and the average daily dose calculated separately in each month since drug initiation) (more details in section 2.6). Incidence of dose reduction/interruption will be defined as average daily dose not following the prescribing information (PI). According to the PI, the daily dose of pirfenidone is 2403 mg [13], hence the study will consider average daily dose less than 2165 mg (90% of PI dose) as dose reduction for pirfenidone [12]. For nintedanib, the daily dose allowed under prescriber information is 200 mg [14], hence less than 200 mg will be considered a dose reduction for nintedanib patients. As a secondary outcome, we will also assess drug discontinuation during first 6 and 12 months separately for pirfenidone and nintedanib and will be defined as a gap of at least 60 days in filling of prescription (a gap of 60 days after the prescription date + days of supply for the current prescription). In a sensitivity analysis, we will explore 30- and 90- days gap as a definition for drug discontinuation. As this is a descriptive study, assessment of the dose reduction and discontinuation for both drugs will be considered separately, and only descriptively, without any direct comparison between the two cohorts.

NIS Protocol Page 16 of 36

Study number: 1199-0526 Document number: c41847952-01

Proprietary confidential information © 2023 Boehringer Ingelheim International GmbH or one or more of its affiliated companies

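### The primary-outcome rule counts on-time nintedanib 200 mg/day as a dose reduction while sections 7 and 9.1 do not, and the monthly dose lacks a rule for allocating fills to months

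*Combined protocol and SAP*

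**What the plan says.** The main outcome is the incidence of dose reduction or temporary interruption, built on an average daily dose (section 9.3.2.1). The only formula given divides all tablets dispensed by the days from index to discontinuation. The section then says "We will calculate average daily dose of pirfenidone and nintedanib separately for each month in post-index period (month 1 to 12", without a monthly version of the formula.

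For nintedanib, section 9.3.2.1 counts as an event an average daily dose ≤66.67% "dose strength (for nintedanib), as per the PI". Section 7 defines the event differently: "or less than a daily dose of 200 mg for nintedanib (66.67% of full dose, which is 300 mg". Section 9.1 agrees with section 7: "hence less than 200 mg will be considered a dose reduction for nintedanib patients". Section 7 also says: "For nintedanib, reducing dose from 150 mg to 100 mg BID is part of the PI".

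The low dose must last at least 60 days, "to make sure that the dose reduction is not temporary". The worked example in section 9.3.2.1 treats this as two months: "dose below label recommendation for the whole month 2 and 3". Section 9.3.2.2 ends follow-up only at a refill gap of 60 days or more and gives typical supply as 30 days. For calculation detail, section 9.1 points elsewhere ("more details in section 2.6"), but the protocol has no such section.

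**The concern.** There are two problems of unequal weight.

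The main one is a contradiction in the primary-outcome rule. The outcome is meant to capture dosing outside the prescribing information, and sections 7 and 9.1 place nintedanib 200 mg/day inside it. Read literally, section 9.3.2.1 counts that dose group as events even when every refill is on time. A programmer working from section 9.3.2.1 and one working from section 9.1 could report different incidences from the same data.

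The second is that the monthly dose cannot be computed without choices the protocol leaves open: how a fill that crosses a month boundary is split, and whether early refills carry forward. Refill gaps under 60 days stay in the denominator. An event can therefore appear or disappear at an unchanged dispensed dose, and a reader cannot tell a lower dispensed dose from late refills. This matters because section 7 already anticipates a finding of sub-optimal pirfenidone dosing.

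**Working it through.** **Inputs.** Full doses are 2403 mg and 300 mg (section 7). Cut-offs are 90% or 2165 mg for pirfenidone, and ≤66.67% or <200 mg for nintedanib (sections 7, 9.1, 9.3.2.1). Fills are 30 days, as is typical in section 9.3.2.2. An event is two consecutive low months from month 2 onwards (sections 9.3.2.1 and 9.7.1).

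**The plan's own figures.** 0.90 × 2403 = 2162.7 mg, and 2165/2403 = 90.1%, so the two pirfenidone forms agree closely. 200/300 = 66.67% to two decimals.

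**Nintedanib boundary.** 0.6667 × 300 = 200.01 mg.
- ≤66.67%: 200 ≤ 200.01, an event.
- <200 mg: 200 < 200 is false, not an event.
- <66.67%: 200 < 200.01, still an event. Changing the sign alone does not reconcile the sections.

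**Late refills at an unchanged dispensed dose.** Assume every refill is late by the same number of days (0 to 29). Two allocation rules are compared: tablets spread over days of supply, and the whole fill booked to the month of the fill date. Two month definitions are compared: 30 days, and calendar months of 28 to 31 days counted from every index date from 15 October 2014 to 30 September 2021 (2,543 dates). Entries show when the 60-day outcome is first met. Percentages are shares of index dates.

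| Dispensed dose and cut-off | Spread, 30-day months | Spread, calendar months | Fill month, 30-day months | Fill month, calendar months |
|---|---|---|---|---|
| Pirfenidone 2403 mg, either form | 3 days late | 3 days: 4.2%; 4 days: 100% | never | never |
| Nintedanib 300 mg, ≤66.67% | 10 days late | 10 days: 1.4%; 11 days: 100% | never | never |
| Nintedanib 300 mg, <200 mg | 11 days late | 10 days: 0%; 11 days: 100% | never | never |
| Nintedanib 200 mg, ≤66.67% | on time | on time: 100% | on time | on time: 100% |
| Nintedanib 200 mg, <200 mg | 1 day late | on time: 0%; 1 day: 100% | never | on time: 98.6% |

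Checks by hand, spread tablets, months 2 and 3 of 30 days:
- Pirfenidone, 3 days late: 27/30 × 2403 = 2162.7 mg in each month, low under both forms.
- Nintedanib 300 mg, 10 days late: 20/30 × 300 = 200 mg in each month, low only under ≤66.67%.
- Nintedanib 300 mg, 11 days late: 19/30 × 300 = 190 mg in each month, low under both.

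The 98.6% arises because one 30-day fill of 200 mg/day in a 31-day month gives 30 × 200/31 = 193.5 mg.

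The nintedanib 300 mg figures are first occurrences, and not every longer delay qualifies. At 20 days late, months 2 to 4 are 10/30, 20/30 and 20/30 of 300 mg, that is 100, 200 and 200 mg. Only month 2 is below 200 mg.

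**Carry-over.** Take full-dose pirfenidone filled on days 0, 25, 50, 75, 110, 145 and 180, then every 30 days. The six fills before day 180 supply 6 × 30 = 180 days. Without carry-over, months 4 to 6 each have 25 covered days: 25/30 × 2403 = 2002.5 mg (83%), an event. With carry-over every month is 2403 mg, no event.

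**The case against.** Several points on the other side stand.

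- Counting interruptions is partly intended. The outcome's name includes them, and section 9.9 discloses that fill-based dose may differ from intake and that reduction and interruption are not separated. Gaps in every cycle for two months may be real under-supply, and a patient who stretches tablets also refills late.
- Thirty-day months are the better supported reading: 60 days is illustrated as two months and fills are typically 30 days, whereas two calendar months can total 28 + 31 = 59 days. The calendar columns are a sensitivity check.
- The ≤ sign may be a drafting slip. The sensitivity definition and the worked example in section 9.3.2.1 both speak of doses below the line. The operative rule still says otherwise.
- Section 9.8 refers to an analysis plan and a data plan that were not supplied. They may hold the allocation rule, so the gap is claimed for this protocol only.

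A reader might infer that the nintedanib wording alone decides the result for every 200 mg/day patient. It does not. Under <200 mg with spread tablets, a patient 1 day late at each refill is flagged anyway. With fill-month booking in calendar months, 98.6% of index dates are flagged even on time.

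A reader might also infer that late refills at full dose always create events. In these scenarios they do so only when tablets are spread over days of supply.

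**Conclusion.** The nintedanib contradiction is definite. With on-time refills, 200 mg/day is an event under section 9.3.2.1. Under sections 7 and 9.1 it is not, provided tablets are spread over days of supply or fills are booked to the fill month in 30-day months. This review takes no position on which cut-off is right.

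The missing allocation and carry-over rule is secondary and mostly a matter of absent detail, but it can reverse a patient's classification. With spread tablets in 30-day months, the outcome is first met at 3 days late for full-dose pirfenidone and at 10 or 11 days for full-dose nintedanib. With fill-month booking it is met by neither at 0 to 29 days.

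These figures assume 30-day fills and identical lateness at every refill, and the carry-over sequence is constructed. The documents give no refill-delay data and do not say how many patients are dispensed 200 mg/day, so they support no estimate of the change in incidence for either drug.

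**What to change.** 1. Reconcile sections 7, 9.1 and 9.3.2.1 on the nintedanib cut-off. State whether 200 mg/day with on-time refills counts, and write the limit in mg or as an exact fraction with one inequality sign.
2. In section 9.3.2.1 give the monthly rule: tablets spread over days of supply, early refills carried forward, and 30-day months to match the 60-day, two-month requirement. Redirect the dead cross-reference in section 9.1 to it.
3. Spreading keeps the sensitivity to late refills. Beside the existing composite, therefore, report dispensed dose per covered day (strength × tablets / days of supply) and gap days under 60.
4. In section 9.9 say that dispensed dose and gaps can be separated although actual intake cannot, and that the composite tolerates late refills unequally by drug and dose.

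The cost is a little programming and a few table rows. Strength, fill date and days of supply are listed in section 9.2.1, and tablets per fill is already needed for the formula. A patient who stretches supply will appear as gap days rather than as a lower dispensed dose, so all three measures should be shown together.
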